8.4.1.1. Serious Adverse Events Reporting

The following types of events should be reported by the Investigator in the electronic data capture (EDC) or on a SAVER (Serious Adverse Event Report) form within 24 hours of awareness:

- SAEs (Section [10.5.2](#))
- Hepatic events (both serious and non-serious) meeting the laboratory criteria of a potential Hy's Law criteria (as defined in Section [8.4.1.2](#))
- Overdose (as defined in Section [8.4.1.1.1](#))

Details summarizing the course of the SAE, including its evaluation, treatment, and outcome should be provided. Specific or estimated dates of AE onset, treatment, and resolution should be included. Medical history, concomitant medications, and laboratory data that are relevant to the event should also be summarized in the SAE report. For fatal events, the SAE report should state whether an autopsy was or will be performed and should include the results if available. Source documents (including medical reports) will be retained at the study site and should not be submitted to the Sponsor for SAE reporting purposes.

If using EDC for SAE reporting: Complete the eCRF within 24 hours of awareness. In the event that the eCRF is unavailable, report SAEs by faxing or emailing the *SAVER Form* to Sponsor or CRO using the provided fax transmittal form and the appropriate fax number provided for the country or email address. Once EDC becomes available, please enter SAEs reported on the SAVER Form into the eCRF as soon as possible. Please refer to the *eCRF Completion Guide* for additional instructions.

Call the local SAE Hotline (see *PL3397-A-U4003 Study Site Manual*) or study monitor for any questions on SAE reporting.

See Section [8.4.1](#) for details on the time period for collecting SAEs.

Reporting Requirement to Sites and Regulatory Authorities

The Sponsor/CRO will inform Investigators and regulatory authorities of any suspected unexpected serious adverse reactions (SUSARs) occurring in study sites or other studies of pexidartinib, as appropriate per institutional and/or local reporting requirements.

The Sponsor and/or CRO will inform Investigators and regulatory authorities of all SAEs, regardless of relatedness, reported from this study, and any Suspected Unexpected Serious

Adverse Event Reactions (SUSARs) occurring in other studies of pexidartinib, as appropriate per institutional/local reporting requirements.

Sponsor or CRO will comply with any additional local safety reporting requirements. The Investigator will assess if an AE is to be considered “unexpected” based on the “Reference Safety Information” section in the current pexidartinib IB.⁶

Follow-up for AEs and SAEs

The Investigator is obligated to perform or arrange for the conduct of supplemental measurements and/or evaluations as medically indicated to elucidate the nature and/or causality of the AE or SAE as fully as possible. This may include additional laboratory tests or investigations, histopathological examinations, or consultation with other health care professionals.

Urgent safety queries must be followed up and addressed promptly. The Investigator will submit any updated SAE data to the Sponsor or CRO within 24 hours of receipt of the information. Follow-up information and response to non-urgent safety queries should be combined for reporting to provide the most complete data possible within each follow-up report.

8.4.1.1.1. Overdose

An overdose is defined as the accidental or intentional administration of any dose of a product that is considered both excessive and medically important. All occurrences of overdose must be reported to **Sponsor and/or CRO** within 24 hours of awareness. Overdose will be reported via the **SAVER/overdose** Form or eCRF.

An “excessive and medically important” overdose includes any overdose in which either an SAE, a non-serious AE, or no AE occurs and is considered by the Investigator as clinically relevant, ie., poses an actual or potential risk to the subject.

Occupational exposures must be reported via the SAVER form.

8.4.1.2. Adverse Events of Special Interest

Pexidartinib can cause serious and potentially fatal liver injury. Hepatotoxicity with ductopenia and cholestasis occurred in patients treated with pexidartinib. Across 768 patients who received pexidartinib in clinical trials, there were 2 irreversible cases of cholestatic liver injury. One patient died with advanced cancer and ongoing liver toxicity and 1 patient required a liver transplant. The mechanism of cholestatic hepatotoxicity is unknown and its occurrence cannot be predicted.

It is unknown whether liver injury occurs in the absence of increased transaminases. Avoid pexidartinib in patients with pre-existing increased serum transaminases; total bilirubin or direct bilirubin (>ULN); or active liver or biliary tract disease, including increased ALP. Taking pexidartinib with food increases drug exposure by 100% and may increase the risk of hepatotoxicity. Administer pexidartinib on an empty stomach, at least 1 hour before or 2 hours after a meal or snack. Monitor liver tests, including AST, ALT, total bilirubin, direct bilirubin, ALP and GGT, prior to initiation of pexidartinib, and as defined within the appropriate SoE for the cohorts (Section 1.3). Withhold and dose reduce, or permanently discontinue pexidartinib based on the severity of the hepatotoxicity (Table 6.3).

Combined Elevations of Aminotransferases and Bilirubin

Hepatic events (both serious and non-serious) which meet the potential Hy's Law criteria defined as an elevated (ALT and/or AST) $\geq 3 \times$ ULN and an elevated TBIL $> 2 \times$ ULN, regardless if it is due to disease progression per Investigator assessment, that may occur at different time points during the study conduct, should always be reported to the Sponsor. These events must be reported either by a SAVER form or eCRF, with the Investigator's assessment of seriousness, severity, causality, and a detailed narrative. These events should be reported within 24 hours of Investigator's awareness of the event regardless of seriousness. A targeted questionnaire will be available as an eCRF to collect relevant additional information for these potential cases.

If the subject discontinues study drug due to liver enzyme abnormalities, the subject will have additional clinical and laboratory evaluations as described in Section 10.2 in order to determine the nature and severity of the potential liver injury.

Additional information can be found in the *PL3397-A-U4003 Study Manual* and the *Pexidartinib IB*.

8.4.2. Pregnancy/Embryo-Fetal Toxicity

Based on animal studies and its mechanism of action, pexidartinib may cause fetal harm when administered to a pregnant woman. Oral administration of pexidartinib to pregnant rats and rabbits during the period of organogenesis resulted in malformations, increased post-implantation loss, and abortion at exposures approximately equal to the human exposure at the recommended dose of 800 mg based on area under the curve (AUC).

Advise pregnant women of the potential risk to a fetus. As pexidartinib is a moderate CYP3A4 inhibitor, concurrent administration of pexidartinib with ethinyl estradiol may lead to reduced exposure of ethinyl estradiol. Females of reproductive potential should be advised to use an effective, non-hormonal method of contraception during treatment with pexidartinib and for 1 month after the last dose. Males with female partners of reproductive potential should be advised to use an effective method of contraception during treatment with pexidartinib and for 1 month after the last dose. Female partners of male patients should concurrently use effective contraceptive methods (hormonal or non-hormonal).

Sponsor must be notified of any female subject or partner of a male subject who becomes pregnant while receiving or within 30 days of discontinuing pexidartinib.

Although pregnancy is not technically an AE, all pregnancies must be followed to conclusion to determine their outcome. If a pregnancy is reported, the Investigator should inform the Sponsor within 24 hours of learning of the pregnancy.

This information is important for both drug safety and public health concerns. It is the responsibility of the Investigator, or designee, to report any pregnancy in a female subject or partner of a male subject using the *Exposure In Utero (EIU) Reporting Form*. Please contact your study monitor to receive the *EIU Reporting Form* upon learning of a pregnancy. The Investigator should make every effort to follow the female subject or partner of a male subject (upon obtaining written consent from partner) until completion of the pregnancy and complete the *EIU Reporting Form* with complete pregnancy outcome information, including normal delivery and induced abortion. Any adverse pregnancy outcome, either serious or non-serious, should be reported in accordance with study procedures. If the outcome of the pregnancy meets

the criteria for immediate classification as an SAE (i.e., post-partum complications, spontaneous or induced abortion, stillbirth, neonatal death, or congenital anomaly, including that in an aborted fetus), the Investigator should follow the procedures for reporting SAEs.

Pregnancy Test

For females of reproductive potential (as defined in Section 5.1), document the results of a negative serum pregnancy test. A positive pregnancy test at Screening will exclude female subject enrollment. Any females enrolled in the study and receiving pexidartinib who become pregnant must discontinue pexidartinib and communicate this information to the Investigator, and have their pregnancy followed to outcome.

8.4.3. Clinical Laboratory Evaluations

The clinical laboratory tests including hematology, coagulation, serum chemistry, TSH and urinalysis will be performed. De-identified laboratory reports with all local laboratory results from samples collected for hematology, coagulation, serum chemistry, TSH, and urinalysis will be collected on the local laboratory form in EDC to be data entered into the clinical database. Refer to Table 10.1 for the complete list of laboratory parameters. Laboratories parameters from the previous pexidartinib studies may be used at Baseline.

Abnormal laboratory values (NCI-CTCAE Grade 3 or 4) occurring during the clinical study will be followed until repeat test results return to normal (or Baseline), stabilize, or are no longer clinically relevant, as determined by the Investigator. New or worsened clinically relevant abnormalities should be recorded as AEs on the Adverse Event eCRF.

8.4.4. Reporting of Exposure to COVID-19 (SARS-CoV-2)

All confirmed or suspected COVID-19 events must be recorded in the eCRF.

- Subjects who test positive for COVID-19 should be reported as “Confirmed COVID-19” either as an AE or serious adverse event (SAE).

The usual protocol mandated SAE reporting requirements should be followed for confirmed or suspected COVID-19 (or SARS-CoV-2) as done for any other AE, ie, the Investigator should assess whether any seriousness criteria are met per protocol, and appropriate protocol reporting requirements should be followed.

In the event that the Investigator assesses that a COVID-19 case does not meet any seriousness criteria as outlined in the protocol, it should be reported as a non-serious AE in the eCRF.

All study drug interruption or dose reduction or discontinuation due to the COVID-19 event must be recorded on the AE and drug administration eCRFs.

For both serious and non-serious COVID-related AEs, the following information should be provided as applicable:

- Date and laboratory results confirming the COVID-19 diagnosis (including viral antigen test and/or antiviral antibody serological test) in the eCRF.

- Clinical course of the case, including presenting signs, symptoms, exposure, actions taken with the investigational products, medications used for treatment or prophylaxis of COVID-19, and outcome in relevant eCRF (eg, concomitant medication, AE).
- Findings from diagnostic imaging (including computed tomography scan or other chest imaging).

8.4.5. Other Safety

Physical Examinations

A complete physical examination should include a weight measurement and an evaluation of the head, eyes, ears, nose, and throat and the cardiovascular, dermatological, musculoskeletal, respiratory, gastrointestinal, genitourinary, and neurological systems. Any abnormality identified at Baseline should be recorded on the General Medical History and Baseline Conditions eCRF. At subsequent visits (or as clinically indicated), limited, symptom-directed physical examinations should be performed. Changes from Baseline abnormalities should be collected in the subject's study record. New or worsened clinically relevant abnormalities should be recorded as AEs on the Adverse Event eCRF.

Vital Signs

Vital signs will include the measurements of respiratory rate, heart rate, systolic and diastolic blood pressures, temperature, height (may be obtained from subject's prior study file), and body weight [for Screening/Baseline this may be obtained from the subject's prior study]. Vital signs should be taken prior to ECG measurement. Blood pressure and pulse rate will be measured after the subject has rested in a recumbent position for at least 5 minutes and prior to laboratory draws.

Electrocardiograms

12 lead-electrocardiograms (ECGs) will be performed and recorded for every subject at Screening. The ECG will be measured after the subject has rested in a recumbent position for at least 5 minutes and the ECG results will be read locally. At any visit during which a subject exhibits a heart rate ≤ 50 bpm or other clinical indications for ECG, the ECG will be repeated. Any abnormal finding should be confirmed with a repeated ECG. Abnormal, clinically relevant findings occurring post-baseline will be reported as AEs. Whether or not the measurement is performed, the date the ECG is to be performed, heart rate, PR interval, RR interval, QRS amplitude, QT interval, QTcF interval, and results will be recorded in the eCRF.

8.5. Pharmacokinetic (PK) Assessment(s)

Not applicable.

8.6. Pharmacodynamic Assessment(s)

Not applicable.

9. STATISTICAL CONSIDERATIONS

9.1. General Statistical Considerations

This is a phase 4, multicenter study to evaluate the discontinuation and re-treatment of pexidartinib in subjects with TGCT (PVNS or GCT TS) who were previously treated with pexidartinib in one of the following studies: (PLX108-10 (ENLIVEN), PLX108-01, PL3397-A-A103, and PL3397-A-U126). There is no statistical hypothesis for this study. The statistical analysis will be descriptive in nature. No p-values will be reported.

9.2. Statistical Hypothesis

Not applicable.

9.3. Sample Size Determination

The study sample size is not based on statistical consideration. Subjects currently enrolled in Studies PLX108-10 (ENLIVEN), PLX108-01, PL3397-A-A103, and PL3397-A-U126 who are eligible can participate in this study.

9.4. Population for Analysis Sets

Analysis Sets

- The Safety Analysis Set will include all subjects who entered this study. Subjects will be analyzed according to their cohort (**Treatment-Free/Re-Treatment Cohort; Treatment Continuation Cohort**).
- The Full Analysis Set (FAS) for the **Treatment-Free/Re-Treatment Cohort** will include all subjects who entered the Treatment-Free/Re-Treatment Cohort. This data set will be the primary population for the primary endpoint.
- The Full Analysis Set (FAS) for the **Treatment Continuation Cohort** will include all subjects who entered the Treatment Continuation Cohort.
- The Evaluable Analysis Set (EAS) will include all subjects who entered the study with Baseline measure and at least 1 post-baseline measures available. The data set will be used for PRO measures.
- The Re-Treatment Analysis Set (RAS) will include all subjects who received at least 1 dose of pexidartinib in the **Treatment-Free/Re-Treatment Cohort** after stopping pexidartinib. The data will be used for both efficacy and safety analyses for re-treated subjects in the **Treatment-Free/Re-Treatment Cohort**.

9.5. Statistical Analysis

The Statistical Analysis Plan (SAP) will be developed and finalized before database lock and will describe the subject populations to be included in the analyses, and procedures for accounting for missing, unused, and spurious data. This section is a summary of the planned statistical analyses of the primary and secondary endpoints.

9.5.1. Efficacy Analyses

Table 3.1 and **Table 3.2** list the primary and secondary endpoints and their corresponding definitions of all endpoints. Additional details for the analysis and censoring rules are noted in the following sections. Detailed censoring rules for the primary and applicable secondary efficacy endpoints will be specified in the SAP.

9.5.1.1. Primary Efficacy Analyses

The primary endpoint in this study is the proportion of subjects who remain treatment-free at Month 12 and Month 24 after entering the Treatment-Free period in the **Treatment-Free/Re-Treatment Cohort**. The primary efficacy analysis will be based on the data from the FAS.

Kaplan-Meier methods will be used to estimate the proportion of subjects who remain treatment-free at Month 12 and Month 24. Estimate of the proportion will be provided with its 95% confidence interval (CI) using Greenwood's formula.

The subjects who resume pexidartinib treatment or died will be considered as an event. The subjects who take subsequent systemic therapy or undergo surgery for the treatment of TGCT will also be counted as an event. The subjects who withdraw consent or lost to follow up will be censored at the last contact date.

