CSF-1R inhibition mechanism of action. These elevations are primarily observed during the first 8 weeks of treatment. The second hepatic adverse reaction, mixed or cholestatic hepatotoxicity, which while rarely serious can be life-threatening, also generally appeared in the first 8 weeks of treatment, however, is uncommon and idiosyncratic in nature.

As noted, long-term follow-up showed further increases in tumor response with continued pexidartinib treatment. For long-term pooled efficacy and safety, 130 patients in ENLIVEN and PLX108-01 received pexidartinib; 47% (61) patients remained on treatment at data cut-off.

Median follow-up from first dose to data cutoff was 23 months (range, 16, 67); median treatment duration was 17 months (range, 1, 60+). Four percent (5) patients discontinued pexidartinib due to progressive disease (PD). Pooled RECIST v1.1-based best overall response (BOR) was 54%, with increased BOR from longer treatment. The safety profile was consistent with earlier reports, with no new safety signals.

Currently, besides the ENLIVEN and PLX108-01 studies, there are 2 additional Phase 1/2 studies (Study PL3397-A-A103 and Study PL3397-A-U126) that are ongoing. The objectives of these 4 pexidartinib studies in TGCT have been met and the investigational sites are to be closed. Eligible subjects from these studies will be included in the subject population for this study.

Refer to the *Pexidartinib Investigator's Brochure (IB)* for additional details and information.

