2.2. Study Rationale

Over time, with daily treatment, many patients on long-term use of pexidartinib in these studies achieved significant tumor responses. In the ENLIVEN study, with the 90-day post-treatment observation period, no cases of rapid tumor regrowth were observed, suggesting that quarterly follow-ups are of adequate frequency to identify any patients, who need to re-initiate their treatment. However, beyond the 3-month post-treatment follow-up in ENLIVEN, there are no data to fully understand the impact of discontinuing pexidartinib treatment in patients with stable and/or residual disease. And, with slow-growing disease like TGCT, 3 months is not sufficient to determine the time when the treatment needs to be restarted. Feasibility of intermittent on-off dosing remains an open medical question.

Patients with TGCT diagnosed early in their lives face potentially several decades of daily treatment. In the real-world setting, subjects and Investigators are faced with decisions surrounding patients' activities of daily living and treatment with pexidartinib for TGCT. Further data are necessary to fully understand the safe and effective discontinuation and re-treatment with pexidartinib therapy in this patient population.

The purpose of this Phase 4 multicenter study in subjects with TGCT previously treated with pexidartinib are two-fold. At the Screening visit/time of consent, the Investigators and subjects are provided the choice to either continue treatment with pexidartinib or discontinue treatment with the possibility of re-initiating pexidartinib treatment at a later time. Findings from this study will provide important prospective discontinuation and re-treatment data with pexidartinib in previously treated subjects with residual disease.

Ultimately, this study will contribute meaningful information to the body of research on pexidartinib treatment for patients with TGCT and the safe and effective discontinuation and re-treatment with pexidartinib therapy.

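### Does the primary Kaplan-Meier interval need a named scale and a rule for an estimate of 100% or 0%?

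*Combined protocol and SAP*

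**What the plan says.** Section 9.5.1.1 defines the primary endpoint as the proportion of the Treatment-Free/Re-Treatment Cohort still treatment-free at Month 12 and at Month 24, estimated by Kaplan-Meier in the Full Analysis Set. Restarting pexidartinib, death, another systemic therapy for TGCT and TGCT surgery all count as events. On censoring it says: "The subjects who withdraw consent or lost to follow up will be censored at the last contact date". On precision it says: "Estimate of the proportion will be provided with its 95% confidence interval (CI) using Greenwood's formula". No scale (plain, log, log-log, logit) is named there or elsewhere, and nothing is said about an estimate of 1 or 0.

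Three other places bear on this:

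- Section 9.5 states that a SAP will be finalized before database lock and adds: "This section is a summary of the planned statistical analyses of the primary and secondary endpoints". Section 9.5.1 says: "Detailed censoring rules for the primary and applicable secondary efficacy endpoints will be specified in the SAP". Neither mentions how intervals are built. The file supplied contains no separate SAP text.
- Section 9.1: "The statistical analysis will be descriptive in nature. No p-values will be reported".
- Section 9.3: "The study sample size is not based on statistical consideration". No expected proportion is given, and section 2.2 says that beyond three months off treatment "there are no data to fully understand the impact of discontinuing pexidartinib treatment in patients with stable and/or residual disease".

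**The concern.** Naming Greenwood's formula looks like a complete specification but settles only the variance. Two things stay open.

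The first is the boundary. If nobody has had an event by the time point, the estimate is 1 and the variance is zero, so the plan taken literally could report 100% with limits of 100% and 100%. That claims certainty from what may be a handful of subjects. If the last subject at risk has an event, the estimate is 0 and the formula divides by zero. Because subjects who leave are censored, this can happen although some never had an event. Choosing a scale cures neither case.

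The second is the scale. In a small cohort with few events the lower limit depends heavily on it, and the plain scale can give an upper limit above 100%.

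The cohort is self-selected and of unplanned size. TGCT is described as slow-growing, so a high treatment-free proportion at Month 12 is conceivable. At stake is the credibility of the only precision statement on the headline result.

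**Working it through.** The plan states no sample size, event count or interval width, so there is no figure of its own to reproduce. The check is of the algebra, and then of how often the problem would arise.

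**Inputs.** From the documents: a 95% interval, Greenwood variance, Months 12 and 24. Assumed, because the documents give neither: cohort sizes of 10 to 61 and true proportions of 0.50 to 0.95. The 61 is the count in section 2.1.2 ("47% (61) patients remained on treatment at data cut-off"). It covers two of the four feeder studies at an earlier cut-off, before any split into cohorts, and is not this cohort's size.

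**Algebra at the boundary.** Greenwood: Var(S) = S² × Σ d/[n(n−d)], where d is the number of events and n the number at risk at each event time.

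- S = 1: every d is 0, so the variance is 0. Plain and log intervals become 100% to 100%. Log-log and logit are undefined.
- S = 0: at the last event n = d, so a term has a zero denominator and no scale gives a usable interval.

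This part of the concern is correct.

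**Chance of an estimate of 1**, without censoring, is Sⁿ (for example 0.9¹⁰ = 0.349). The exact lower limit with zero events is 0.025^(1/n) (for example 0.025^(1/10) = 0.692).

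| n | true 0.90 | true 0.80 | true 0.70 | exact lower limit, 0 events |
|---|---|---|---|---|
| 10 | 35% | 11% | 2.8% | 69% |
| 15 | 21% | 3.5% | 0.5% | 78% |
| 20 | 12% | 1.2% | 0.1% | 83% |
| 30 | 4% | 0.1% | 0% | 88% |
| 40 | 1.5% | 0% | 0% | 91% |
| 61 | 0.2% | 0% | 0% | 94% |

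An estimate of 0 while some subjects never had an event is rarer at plausible values. With n = 10 and an assumed 20% dropout by Month 24, it occurs in 0.4% of simulated cohorts at a true proportion of 0.50. It reaches 4.3% and 10.7% only at 0.30 and 0.20.

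**Scale away from the boundary.** Take 1 event in 10, so S = 0.9, with SE(log S) = √[(1−S)/(nS)] = √(0.1/9) = 0.1054.

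- Plain: 0.9 ± 1.96 × √(0.9 × 0.1/10) = 0.9 ± 0.186, or 71.4% to 108.6%.
- Log-log: exp{−exp[log(−log 0.9) ± 1.96 × 0.1054/0.10536]}, or 47.3% to 98.5%.
- Logit: logit(0.9) ± 1.96 × 0.1054/0.1, back-transformed, or 53.3% to 98.6%.
- Exact binomial, for comparison: 55.5% to 99.7%.

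The lower limits differ by 71.4 − 47.3 = 24.1 points. With 10 events in 20 the gap is small: 28.1% to 71.9% (plain) against 27.1% to 69.2% (log-log).

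**Coverage with an exact interval already used at the boundary.** Exact enumeration over 36 combinations (n = 10, 15, 20, 30, 40, 61; true 0.50, 0.60, 0.70, 0.80, 0.90, 0.95) gives:

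- plain 85.0% to 99.9%, log-log 91.4% to 97.4%, logit 91.4% to 98.9%;
- plain for n of 20 or more at 0.50 to 0.70: 92% to 96%.

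The low plain values owe much to the lumpiness of the binomial: at 0.90, coverage is 99.8% at n = 20, 85.1% at n = 30 and 91.4% at n = 40. With 20% dropout assumed, the lowest plain value at true proportions of 0.70, 0.80 and 0.90 is 90.3%, and log-log stays at 94.6% to 96.6%.

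**The case for a change.** The best case for a change runs as follows. The gap is certain, it sits on the primary endpoint, and two or three sentences would close it. The study is open-label, so an analyst who chooses the scale after seeing the data could move the lower limit by 24 points in the 1-in-10 example. At a true proportion of 0.90 and n = 10, a plain interval with no fallback misses the truth in 35.0% of cohorts, and 34.9 of those points are zero-event cohorts. Section 9.5.1 expressly defers censoring rules to the SAP but not interval construction, so one cannot be sure the SAP will deal with it.

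The algebra stands, and so does the point that the choice is better made before database lock than after. The inference that the plan must change does not. Section 9.5 does not offer itself as the full specification, and a transformation and a zero-event convention are ordinary SAP content. The plan never says the plain scale will be used, so the poor coverage figures test an assumed choice. The large zero-event chances need about 20 or fewer subjects together with a true proportion near 0.90. Nothing in the documents makes that the central case: the event definition is broad, and restarting is open to the subject and investigator at every visit.

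Nor is there one clearly better rule to write in. Log-log with an exact fallback gives a lower limit of 69.2% with no events in 10 and 47.3% with one, an abrupt step in the setting that prompts the worry. An exact interval throughout narrows the step to 69.2% and 55.5%, but Clopper-Pearson applies only if nobody is censored; otherwise a beta-product interval is needed. The choice is best made once the cohort size and amount of censoring are known, and the SAP can still make it before lock.

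**Conclusion.** No change to the plan. Section 9.5.1.1 leaves the scale open and Greenwood's formula fails at 1 and 0, but this is missing detail in a summary, and the analyst will fill it in the SAP. A zero-width or undefined interval is visible on the output, and an exact or beta-product interval is the natural replacement.

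The effect is confined to how precision is reported. There is no hypothesis, p-value or decision rule, and the Kaplan-Meier estimate is the same on any scale. On the assumed inputs it matters mainly for about 20 or fewer subjects with a true proportion near 0.90 or above. It is small for n of 20 or more at 0.50 to 0.70, and negligible near 60 unless the proportion is extreme. This rests on a cohort size and restart rate that the documents do not give, and on the SAP being written before database lock as section 9.5 promises.
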